6.2. Preparation/Handling/Storage/Accountability

Guselkumab, placebo for guselkumab, golimumab, and placebo for golimumab will be supplied to the study sites. All study interventions must be stored according to the labeled storage condition, 2°C to 8°C (36°F to 46°F), and protected from exposure to light. Do not freeze the study interventions. The products are designed for single-use only.

Guselkumab should be clear and colorless to light yellow solution that may contain small translucent particles. Do not use guselkumab if the liquid is cloudy or discolored, or has large

particles. Golimumab should be clear to slightly opalescent and colorless to light yellow. Do not use golimumab if the solution is discolored or cloudy, or if foreign particles are present. Protection from light is not required during the preparation and administration of the study intervention material; avoid direct exposure to sunlight. Aseptic procedures must be used during the preparation and administration of the study intervention material.

Refer to the site IPPM and IPPI for additional guidance on study intervention preparation, handling, and storage.

6.2.1. Accountability

The investigator is responsible for ensuring that all study intervention received at the site is inventoried and accounted for throughout the study. The study intervention administered to the participant must be documented on the intervention accountability form. All study intervention will be stored and disposed of according to the sponsor's instructions.

Study intervention must be handled in strict accordance with the protocol and the container label, and must be stored at the study site in a limited-access area or in a locked cabinet under appropriate environmental conditions. Unused study intervention must be available for verification by the sponsor's study site monitor during on-site monitoring visits. The return to the sponsor of unused study intervention will be documented on the intervention return form. When the study site is an authorized destruction unit and study intervention supplies are destroyed on-site, this must also be documented on the intervention return form.

Potentially hazardous materials such as used ampules, needles, syringes, and vials containing hazardous liquids should be disposed of immediately in a safe manner and therefore will not be retained for intervention accountability purposes.

Study intervention should be dispensed under the supervision of the investigator or a qualified member of the study-site personnel, or by a hospital/clinic pharmacist. Study intervention will be supplied only to participants participating in the study. Returned study intervention must not be dispensed again, even to the same participant. Study intervention may not be relabeled or reassigned for use by other participants. The investigator agrees neither to dispense the study intervention from, nor store it at, any site other than the study sites agreed upon with the sponsor.

6.3. Measures to Minimize Bias: Randomization and Blinding

Randomization will be used to minimize bias in the assignment of participants to treatment groups, to increase the likelihood that known and unknown participant attributes (eg, demographic and baseline characteristics) are evenly balanced across treatment groups, and to enhance the validity of statistical comparisons across treatment groups. Blinded treatment will be used to reduce potential bias during data collection and evaluation of clinical endpoints.

Intervention Allocation

Central randomization will be implemented in this study. Participants will be randomly assigned to 1 of 3 intervention groups (1:1:1 ratio), based on a computer-generated randomization

schedule prepared before the studies by or under the supervision of the sponsor. The randomization will be balanced by using randomly permuted blocks and will be stratified by concomitant use of corticosteroids at baseline (Y/N). The interactive web response system (IWRS) will assign a unique treatment code, which will dictate the treatment assignment and matching study intervention kit(s) for the participant. The requestor must use his or her own user identification and personal identification number when contacting the IWRS, and will then be given the relevant participant details to uniquely identify the participant.

Blinding

To maintain the study blind, the study intervention container will have a label containing the study name, study intervention number, and reference number. The study intervention number will be entered in the eCRF when the study intervention is dispensed. Each active study intervention and its matching placebo will be identical in appearance.

The investigator will not be provided with randomization codes. The codes will be maintained within the IWRS, which has the functionality to allow the investigator to break the blind for an individual participant.

Data that may potentially unblind the treatment assignment (eg, study intervention serum concentrations, antibodies to study intervention) will be handled with special care to ensure that the integrity of the blind is maintained and the potential for bias is minimized. This can include making special provisions, such as segregating the data in question from view by the investigators, clinical team, or others as appropriate until the study unblinding.

The post-baseline results of CRP and fecal calprotectin tests performed by the central laboratory will be blinded to the study sites. If a study site requests these data, it will be provided to them after the final safety analyses have been completed.

Treatment assignment blinding will be maintained for study sites, site monitors, and participants until the final safety DBL and analyses are completed.

In this study, the full sponsor unblinding will occur after the Week 38 DBL. However, a planned interim analysis will occur after the first 30% to 60% of randomized participants have either completed the Week 12 visit or have terminated study participation before Week 12. At the time of this interim analysis, a limited number of sponsor personnel (except for site monitors, who have interactions with the investigative sites) will become unblinded to only those first 30% to 60% of randomized participants. The purpose and analytical details for this interim analysis are provided in Section 9.5. After all 210 randomized participants have either completed the Week 12 visit or have terminated study participation before Week 12, the Week 12 DBL will occur and the data for participants will be unblinded and released for analysis to a limited number of sponsor personnel (except for site monitors, who have interactions with the investigative sites). A subsequent Week 38 DBL will occur when all 210 randomized participants have either completed the Week 38 visit or have terminated study participant before Week 38. Following the Week 38 DBL, the treatment assignment information will be unblinded to the sponsor for all participants and released to the sponsor for analysis. The final safety DBL

will occur when all randomized participants have either completed the final safety visit or have terminated study participation. Additional DBLs may occur as needed.

Identification of sponsor personnel who will have access to the unblinded participant-level data at the time of each DBL will be documented before unblinding.

Under normal circumstances, the investigator blind should not be broken unless specific emergency treatment/course of action would be dictated by knowing the treatment status of the participant. In such cases, the investigator may in an emergency determine the identity of the treatment via the IWRS. It is recommended that the investigator contact the sponsor or its designee, if possible, to discuss the particular situation before breaking the blind. Telephone contact with the sponsor or its designee will be available 24 hours per day, 7 days per week. If the blind is broken, the sponsor must be informed as soon as possible. The date and reason for the unblinding must be documented in the appropriate section of the eCRF and in the source document. The documentation received from the IWRS indicating the code break must be retained with the participant's source documents in a secure manner.

Additionally, a given participant's treatment assignment may be unblinded to the sponsor, the Independent Ethics Committee/Institutional Review Board (IEC/IRB), and site personnel to fulfill regulatory reporting requirements for suspected unexpected serious adverse reactions (SUSARs). If a participant is unblinded by the site, the information must be entered in the appropriate section of the eCRF and in the participant's source documents.

Participants who have had their treatment assignment unblinded by the investigator will not be eligible to receive further study intervention, but should complete evaluations specified in the appropriate SoA (Section 1.3) for participants who discontinue study intervention.

A separate code break procedure will be available for use by J&J Global Medical Safety group to allow for unblinding of individual participants to comply with specific requests from regulatory or health authorities.

6.4. Study Intervention Compliance

When study intervention is administered as an IV infusion or SC injection by qualified staff, the details of each administration will be recorded in the eCRF. For IV infusions, this will include date and start and stop times of the IV infusion and volume infused; for SC injections, this will include date and time of SC injection. Additional details may be provided in the site IPPM and IPPI that is provided separately.

Compliance with the treatment schedule is strongly encouraged. Throughout the study, the investigator or designated study research personnel will be responsible for providing additional instruction to re-educate any participant who is not compliant with taking study intervention.

6.5. Concomitant Therapy

Prestudy therapies administered up to 30 days before the first administration of study intervention must be recorded on the eCRF. Concomitant therapies must be recorded throughout the study, from signing of the informed consent to the last study visit.

All therapies (prescription or over-the-counter medications, including vaccines, vitamins, herbal supplements; non-pharmacologic therapies such as electrical stimulation, acupuncture, special diets, exercise regimens) different from the study intervention must be recorded in the eCRF. Recorded information will include a description of the type of therapy, treatment period, dosage, route of administration, and indication. Modification of an effective pre-existing therapy should not be made for the explicit purpose of entering a participant into the study.

6.5.1. Concomitant Medications

Immunomodulators (6-MP, AZA, and MTX) must be discontinued 2 weeks prior to the first dose of study intervention, as defined in the Inclusion Criteria (Section 5.1). Participants who are receiving oral 5-ASA compounds or oral corticosteroids for the treatment of UC at baseline should maintain a stable dose for the specified period before baseline, as defined in the Inclusion Criteria (Section 5.1). In general, participants who are receiving these medications for UC at baseline (ie, Week 0) should maintain a stable dose through Week 38, with the exception of oral corticosteroids. Therapies can only be discontinued or reduced in dose after Week 0 if investigator judgment requires it because of toxicity or other medical necessity; even if the toxicity resolves, the therapy should not be restarted. Oral corticosteroids must be maintained at baseline doses through Week 6, and all participants must begin tapering oral corticosteroids at Week 6, unless medically not feasible (see further details in Section 6.5.1.1, Oral Corticosteroids Tapering).

Enrolled participants **should not initiate** any of the following concomitant UC-specific medical therapies:

- Oral or rectal 5-ASA compounds.
- Oral, parenteral, or rectal corticosteroids, including budesonide and beclomethasone dipropionate.
- Antibiotics as a primary treatment for UC.
- Total parenteral nutrition or enteral nutrition as a treatment for UC.

If the above medical therapies are initiated or medication doses are changed based on medical necessity as assessed by the investigator, participants should continue to attend all study visits and have all assessments. While this does not represent a deviation from the study protocol and the participants may remain on their assigned therapy, it may be considered a treatment failure. Treatment failures due to UC medication changes will be defined in the SAP.

6.5.1.1. Oral Corticosteroids Tapering

At Week 6, all participants who were taking oral corticosteroids at Week 0 must begin tapering corticosteroids. This tapering is mandatory, unless not medically feasible, and should follow the

recommended schedule shown in [Table 3](#). If participants experience worsening of their disease activity while tapering corticosteroids, further dose decreases may be suspended, and/or their oral corticosteroid dose may be temporarily increased if deemed necessary by the investigator. The oral corticosteroid dose, however, may not be increased above the Week 0 dose unless due to medical necessity. For participants whose corticosteroid taper is interrupted, investigators are encouraged to resume tapering within 4 weeks. Tapering may exceed this schedule only if warranted by medical necessity (eg, participant experiencing corticosteroid-related side effects).

Table 3: Recommended Tapering Schedule for Oral Corticosteroids	
Recommended Tapering Schedule for Oral Corticosteroids (Other than Oral Budesonide and Oral Beclomethasone dipropionate)	
Dose >15 mg/day prednisone or equivalent:	Taper daily dose by 5 mg/week until receiving 10 mg/day, then continue tapering by 2.5 mg/week until 0 mg/day
Dose 11 to 15 mg/day prednisone or equivalent:	Taper daily dose to 10 mg/day for 1 week, then continue by 2.5 mg/week until 0 mg/day
Dose ≤10 mg/day prednisone or equivalent:	Taper daily dose by 2.5 mg/week until 0 mg/day
Recommended Tapering Schedule for Oral Budesonide and Oral Beclomethasone dipropionate	
Participants receiving oral budesonide or oral beclomethasone dipropionate should have their daily dose tapered according to local clinical practice until 0 mg/day	

6.5.2. Prohibited Concomitant Medications

Participants who initiate the following treatments during study participation will have their study intervention discontinued:

- Immunomodulatory agents (including, but not limited to, 6-MP, AZA, MTX, tofacitinib, 6-thioguanine, cyclosporine, mycophenolate mofetil, tacrolimus, and sirolimus).
- Immunomodulatory biologic agents (including, but not limited to, TNF antagonists, ustekinumab, vedolizumab, abatacept, anakinra).
- Experimental IBD medications (including, but not limited to, upadacitinib, filgotinib, ozanimod, etrolizumab, brazikumab, mirikizumab, risankizumab) or other investigational therapies.
- Thalidomide or related agents.

The sponsor or designee must be notified in advance (or as soon as possible thereafter) of any instances in which prohibited therapies are administered.

As protection of human research participants is paramount, it is recognized that initiating such therapies may rarely be required due to medical necessity. However, initiation of these prohibited medications should be documented as a deviation from the study protocol, and participants will be discontinued from receiving further study intervention (Section 7).

Participants who discontinue study intervention administration should complete the appropriate visit(s) as described in Section 1.3.

Note: Participants must not receive guselkumab or golimumab outside of the protocol or participate in any other clinical study with an investigational agent while in this study, and must terminate study participation if they do. Prior to termination of study participation, participants should complete the appropriate visit(s) as described in Section 1.3.

6.6. Dose Modification

No dose adjustment of study intervention will be permitted during the study.

6.7. Intervention After the End of the Study

This protocol is designed to provide participants with up to approximately 38 weeks of treatment.

Participants will be instructed that study intervention will not be made available to them after they have completed/discontinued study intervention and that they should return to their primary physician to determine standard of care.

7. DISCONTINUATION OF STUDY INTERVENTION AND PARTICIPANT DISCONTINUATION/WITHDRAWAL

If a participant discontinues study intervention or withdraws from the study before the end of the study, assessments should be obtained as specified in the SoA (Section 1.3).

7.1. Discontinuation of Study Intervention

A participant who discontinues study intervention will not be automatically withdrawn from the study (see Section 7.2).

A participant's study intervention must be discontinued under the following conditions:

1. The participant initiates treatment with prohibited concomitant medication(s) (Section 6.5.2).
2. The participant has a colectomy.
3. The participant becomes pregnant or plans a pregnancy within the study period. Refer to Appendix 4 (Section 10.4), Contraceptive and Barrier Guidance and Collection of Pregnancy Information.
4. The participant (or the participant's legally acceptable representative) withdraws consent for administration of study intervention.
5. The participant develops an opportunistic infection.

6. The participant is deemed ineligible according to the following TB screening criteria:
- A diagnosis of active TB is made.
 - A participant has symptoms suggestive of active TB based on follow-up assessment questions and/or physical examination, or has had recent close contact with a person with active TB, and cannot or will not continue to undergo additional evaluation.

A participant undergoing evaluation has a chest radiograph with evidence of current active TB and/or a positive or indeterminate QuantiFERON[®]-TB test result (and/or a positive tuberculin skin test result in countries in which the QuantiFERON[®]-TB test is not approved/registered or the tuberculin skin test is mandated by local health authorities).

Note: In Ukraine, while the QuantiFERON[®]-TB test is not approved/registered, it is accepted and a tuberculin skin test is not required.

7. Criterion modified per Amendment 2.

7.1. The participant has a serious adverse reaction that is related to an injection or an infusion, including an injection-site or infusion reaction, resulting in bronchospasm with wheezing and/or dyspnea that requires ventilatory support **OR** that results in symptomatic hypotension with a decrease in systolic blood pressure >40 mm Hg or blood pressure <90/60 mm Hg.

8. The participant has a reaction resulting in myalgia and/or arthralgia with fever and/or rash (suggestive of serum sickness and not representative of signs and symptoms of other recognized clinical syndromes) occurring 1 to 14 days after an injection of study intervention. These may be accompanied by other events including pruritus, facial, hand, or lip edema, dysphagia, urticaria, sore throat, and/or headache.
9. The participant has severe hepatic function abnormalities, as described in Section 8.2.5 and Appendix 7 (Section 10.7).
10. The participant is diagnosed with a malignancy including squamous cell skin cancer. Consideration may be given to allowing participants who develop ≤ 2 basal cell skin cancers that are adequately treated with no evidence of residual disease to continue to receive study intervention.
11. The participant develops congestive heart failure.
12. The participant is diagnosed with a demyelinating disorder.
13. The participant develops symptoms suggestive of a lupus-like syndrome and is positive for antibodies against double-stranded DNA.
14. The investigator believes that for safety or tolerability reasons, it is in the best interest of the participant to discontinue study intervention.

Discontinuation of a participant's study intervention must be strongly considered under the following conditions:

1. Persistent inadequate response or worsening of UC based on signs, symptoms, and/or laboratory values. If the participant experiences AEs consistent with clinically significant worsening of UC at any time during the study, these events should be evaluated by the investigator and the study medical monitor to decide on discontinuation of study

intervention. Discontinuation of study intervention should be considered in participants with clinically significant worsening of UC where continuation of the study intervention is not in the best interest of the participant.

2. Criterion modified per Amendment 2.

2.1. The participant develops a serious infection, including but not limited to sepsis or pneumonia.

Note: Any serious infection should be discussed with the medical monitor or designee, and study intervention should be withheld until the clinical assessment is complete.

3. The participant reports suicidal ideation with intention to act (“Ideation level 4”), suicidal ideation with specific plan and intent (“Ideation level 5”), or any suicidal behavior (actual suicide attempt, interrupted suicide attempt, aborted suicide attempt, or preparatory behaviors for making a suicide attempt) on a post-baseline C-SSRS assessment. If a participant can be adequately treated with psychotherapy and/or pharmacotherapy based on an evaluation by a mental health professional, then the participant, at the discretion of the investigator, may be continued with treatment if agreed to by the medical monitor or designee. Discussion of such participants with the medical monitor or designee is required (see Section 8.2.6).

4. Criterion deleted per Amendment 2.

5. The participant has hematology abnormalities as described below:

- Two sequential absolute neutrophil counts $<0.75 \times 10^3/\mu\text{L}$ (SI: $<0.75 \times 10^9/\text{L}$)
- Two sequential absolute lymphocyte counts $<0.5 \times 10^3/\mu\text{L}$ (SI: $<0.5 \times 10^9/\text{L}$)
- Two sequential hemoglobin values $<8.0 \text{ g/dL}$ (SI: $<80.0\text{g/L}$) or a decrease of $>30\%$ from baseline
- Two sequential platelet counts $<75 \times 10^3/\mu\text{L}$ (SI: $<75 \times 10^9/\text{L}$)

Note: These laboratory abnormalities should be discussed with the medical monitor or designee, and study intervention should be withheld until the clinical assessment is complete.

6. The participant develops a severe injection-site or infusion reaction.

If a participant discontinues study intervention for any reason before the end of the treatment period, assessments should be obtained as specified in the SoA (Section 1.3). If the reason for withdrawal from the study is withdrawal of consent, every effort should be made to conduct the early termination assessments, as indicated in the SoA, prior to terminating study participation. After termination of study participation, no additional assessments are allowed.

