8.2.9. Hypersensitivity Reactions

Before any SC injection or IV infusion of study intervention, appropriately trained personnel and medications must be available to treat hypersensitivity reactions, including anaphylaxis. All participants must be observed carefully for signs and symptoms of a hypersensitivity reaction (eg, urticaria, pruritis, angioedema, wheezing, dyspnea, or hypotension).

In the case of anaphylaxis, injectable epinephrine (intramuscular), respiratory assistance, and other proper resuscitative measures are essential and must be available at the study site where the injections or infusions are being administered.

Participants who experience serious adverse reactions related to an injection or infusion must strongly be considered to be discontinued from further study intervention administrations.

Participants who experience reactions following an injection or infusion that result in bronchospasm with wheezing and/or dyspnea that requires ventilatory support, or symptomatic hypotension with a decrease in systolic blood pressure greater than 40 mm Hg or blood pressure <90/60 mm Hg must be discontinued from additional study intervention administration (see Section 7).

Participants who experience reactions suggestive of serum sickness (resulting in symptoms such as myalgia and/or arthralgia with fever and/or rash that are not representative of signs and symptoms of other recognized clinical syndromes) occurring 1 to 14 days after administration of study intervention, must be discontinued from further study intervention administration. Note that these signs and symptoms may be accompanied by other events including pruritus, facial, hand, or lip edema, dysphagia, urticaria, sore throat, and/or headache.

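### Protocol Sections 7.1 and 8.2.9 give different triggers for the same two mandatory stops: serum-sickness-like reactions, and bronchospasm or symptomatic hypotension

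*Protocol*

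**What the plan says.** **Serum-sickness-like reaction (mandatory stop in both sections).** Protocol Section 7.1 item 8 applies to a reaction "occurring 1 to 14 days after an injection of study intervention". Section 8.2.9 applies to one "occurring 1 to 14 days after administration of study intervention, must be discontinued from further study intervention administration".

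**Bronchospasm or symptomatic hypotension (mandatory stop in both sections).** Protocol Section 7.1 item 7, numbered 7.1 since Amendment 2, reads "The participant has a serious adverse reaction that is related to an injection or an infusion, including an injection-site or infusion reaction, resulting in bronchospasm", and then gives the hypotension limb. Section 8.2.9 begins "Participants who experience reactions following an injection or infusion that result in bronchospasm with wheezing and/or dyspnea that requires ventilatory support", gives the same hypotension limb, requires a stop, and refers to Section 7.

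**Dosing schedule (Section 6.1).** Every arm has active or placebo infusions at Weeks 0, 4 and 8. Through Week 12, every arm has active or placebo subcutaneous (SC) injections at Weeks 0, 2, 6 and 10. No injection is given at Week 4 or Week 8. Table 1 footnote a allows each visit to move by 4 days either way.

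**Analysis (SAP Section 5.3.2).** Stopping treatment for a reason other than lack of efficacy, worsening of ulcerative colitis, or a COVID-19-related reason other than infection is intercurrent event category 5. In the primary estimand it is handled by treatment policy.

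**The concern.** Section 7.1 is the list a site would naturally consult when deciding whether a participant must stop. Section 4.3.3 cites the stopping rule in Section 7 as part of the case that the risk of the combination is manageable. If that list and Section 8.2.9 give different triggers for the same event, two sites could handle the same reaction differently and each could point to a sentence in the protocol.

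The injection wording matters because injections and infusions alternate after Week 0, so an injection-based count leaves out the periods that follow an infusion alone. Guselkumab is given by infusion in two of the three arms during this phase, and blinded sites apply the rule in all three.

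Discontinuation status also feeds into the data. It sets the intercurrent-event category. It moves the Week 12 assessments to the time of discontinuation (Protocol Table 1 footnote c). It removes later samples from the by-visit pharmacokinetic summaries (SAP Section 7.1.1.1).

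**Working it through.** The plan states no figure to reproduce. The check counts days for the first rule and compares wording for the second.

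**Does *injection* in Section 7.1 item 8 include infusions?** The item just before it names both routes: "The participant has a serious adverse reaction that is related to an injection or an infusion". Sections 6.1 and 6.4 and the opening of Section 8.2.9 also keep SC injection and IV infusion apart. The natural reading of item 8 is therefore SC only.

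**Day count, nominal schedule.** Take dosing day = 7 × week, and a window of days +1 to +14.

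- Injection days: 0, 14, 42 and 70.
- Injection windows: days 1–14, 15–28, 43–56 and 71–84.
- Days covered by the injection wording: 4 × 14 = 56 of the first 84.
- Days not covered: 84 − 56 = 28.

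| Infusion | Day | Days +1 to +14 | Covered by the injection wording | Covered by the administration wording |
|---|---|---|---|---|
| Week 0 | 0 | 1–14 | 14 of 14 (injections the same day) | 14 of 14 |
| Week 4 | 28 | 29–42 | 0 of 14 | 14 of 14 |
| Week 8 | 56 | 57–70 | 0 of 14 | 14 of 14 |

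The 28 uncovered days are exactly 29–42 and 57–70. With the administration wording all 84 days are covered. From Week 10 on every dose is an SC injection, so the two wordings then coincide.

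**Day count with ±4-day visits.** Let the Week 2, 4 and 6 visits fall on days 14 + a, 28 + b and 42 + c, each shift between −4 and +4.

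- The days between the two injection windows run from 29 + a to 42 + c.
- The post-infusion window runs from 29 + b to 42 + b.
- Both always contain days 33–38, because 29 + 4 = 33 and 42 − 4 = 38. At least 6 days are therefore missed.
- At most all 14 are missed.

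The same argument for Week 8 gives days 61–66 as always missed. Enumerating every combination of shifts gives 6 to 14 days for each of the two infusions, so the difference never closes.

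**Bronchospasm or hypotension, side by side.**

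| Condition | Section 7.1 item 7 | Section 8.2.9 |
|---|---|---|
| Must be serious | Yes | No |
| Must be related to dosing | Yes | No; need only follow it |
| Clinical outcome required | Same | Same |
| Consequence | Mandatory stop | Mandatory stop, with a reference to Section 7 |

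Under Appendix 9, a reaction needing ventilatory support would normally count as serious (life-threatening or medically important). The seriousness condition therefore changes little for bronchospasm. Symptomatic hypotension that meets the blood-pressure limits without being serious is the case in which the sections part.

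**Effect on the estimands.** A reaction-related stop is category 5.

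- Estimand 1: observed Week 12 status is used if available, as it is for a participant with no intercurrent event. The category alone changes no response value.
- Estimand 2 (composite): the participant becomes a non-responder.
- Estimand 3 (hypothetical): Week 12 status is set to missing and imputed.

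**The case against.** The strongest answer is that the rules are cumulative. Section 8.2.9 is mandatory in its own right, and Section 7.1 does not claim to be the only source of stop conditions. A site that follows the whole protocol has no uncovered day. Section 7.1 item 14 also requires a stop whenever the investigator judges it best for safety or tolerability. This stands. A reader might infer from the day count that participants have no stop rule after the Week 4 and Week 8 infusions; the documents do not support that. The 28 days lie outside one sentence's wording. They are not days without protection, nor a count of affected participants.

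A reader might also infer that the wording alters the primary result through the intercurrent-event category. It does not by rule, since category 5 is handled by treatment policy. An indirect route remains, through missed doses or Week 12 assessments brought forward, but the documents give no event rate from which to size it.

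A third tempting reading is that the rules for considering a stop also conflict: Section 7.1 has "The participant develops a severe injection-site or infusion reaction", and Section 8.2.9 has "Participants who experience serious adverse reactions related to an injection or infusion must strongly be considered to be discontinued". Appendix 9 does define severity and seriousness separately. But these are two compatible prompts for the same discretionary decision, and both can apply, so this is not a contradiction.

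Finally, the reference from Section 8.2.9 to Section 7 could be taken to make Section 7.1 the governing text for bronchospasm and hypotension. That leaves the reader unsure whether Section 8.2.9 is a separate, broader rule or shorthand for the narrower one. The reference therefore does not resolve the mismatch.

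**Conclusion.** The inconsistency is real and confined to two mandatory-stop rules.

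- **Serum-sickness-like reaction:** Section 7.1 item 8, read alone, omits 14 days after each of the Week 4 and Week 8 infusions on the nominal schedule, or 6 to 14 days with shifted visits. Section 8.2.9 covers those days.
- **Bronchospasm or symptomatic hypotension:** Section 7.1 adds seriousness and relatedness conditions that Section 8.2.9 lacks. The practical difference is mainly non-serious symptomatic hypotension.

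The count assumes that *injection* means the SC route, which the protocol's own usage supports, and that doses fall within the stated visit windows. The primary estimand is unaffected by rule. Estimands 2 and 3 are sensitive to who is recorded as having stopped. This is a consistency fault in safety text, not a missing safeguard. It is worth correcting because sites need one trigger per mandatory stop.

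**What to change.** Reconcile Protocol Section 7.1 items 7 and 8 with Section 8.2.9 so that each mandatory-stop trigger reads identically in both places. Three points need a single answer: the dosing route that starts the 14-day count, whether the bronchospasm or hypotension reaction must be serious, and whether it must be related to dosing. The sponsor's medical team should decide these; this review does not say which wording is right. One way to prevent later drift is to state each rule once and have the other section refer to it.

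The *severe* and *serious* wording of the rule for considering a stop can be tidied in the same edit.

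The cost is a protocol clarification or a letter to sites. Assessments do not change, and neither the sample size nor the SAP needs revision.
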